6.1 Primary Data Analysis

The primary analysis cohort consists of patients whose largest exodeviation by PACT at distance, near, or remote distance at the enrollment exam is between 15 and 40 PD inclusive.

The primary analysis will be a treatment group comparison of the proportion of patients with surgical failure by 3 years (*section 6.1.1.*). The primary analysis is stratified by IXT type (basic type and pseudo divergence excess type).

The cumulative proportion of patients meeting criteria for failure by 3 years will be obtained using the Kaplan-Meier method and compared between treatment groups using the Z test. This will allow patients who drop out prior to 3 years to contribute to the estimation of the proportion of surgical failure at 3 years. In this analysis, all patients who meet surgical failure criteria prior to 3 years will be counted as failures at the first visit at which surgical failure criteria are met. The primary analysis will follow the intent-to-treat principle.

6.1.1 Classification of Outcome

At the 3-year visit, each patient's condition will be classified as either surgical failure, success, or indeterminate as follows:

Failure = ANY of the following criteria are met at a visit 6 months or later:

1. Exotropia at distance OR near at any time during the exam (i.e., can be constant or intermittent; determined by a cover/uncover test) with a magnitude of at least 10 PD by SPCT, confirmed by a retest
2. Constant esotropia at distance OR near (determined by at least 3 cover/uncover tests—one must be before any dissociation) with a magnitude of at least 6 PD by SPCT, confirmed by a retest
3. Decrease in Preschool Randot near stereoacuity at least 2 octaves (at least 0.6 log arcsec) (*see Table 3*) from the enrollment measurement, or to nil, confirmed by a retest
4. Reoperation or treatment with botulinum toxin

Success = ALL of the following criteria are met at the 3-year visit:

1. Exodeviation less than 10 PD (tropia or phoria) by PACT at distance and near and reduction of more than 10 PD from largest of distance and near angles at enrollment
2. Esotropia less than 6 PD at distance and near by SPCT
3. No decrease in Preschool Randot stereoacuity of 2 or more octaves from the enrollment stereoacuity and no drop to nil
4. No reoperation or treatment with botulinum toxin
5. No non-surgical treatment for IXT during the study

Indeterminate = ALL of the following criteria are met at the 3-year visit:

1. Patient meets one or more of the following:

- 1439
- Exophoria ≥ 10 PD by PACT at distance or near
 - Exodeviation less than 10PD by PACT at distance and near but no reduction of more than 10 PD from largest of distance and near angles at enrollment
 - Intermittent esotropia or esophoria ≥ 6 PD at distance and/or near
- 1443 2. No decrease in Preschool Randot stereoacuity of 2 or more octaves from the enrollment stereoacuity or a drop to nil
- 1444
- 1445 3. No reoperation or treatment with botulinum toxin
- 1446

1447 **6.2 Secondary Data Analysis**

1448 All secondary analyses will be conducted on the primary cohort and stratified by IXT type.

1449

1450 **6.2.1 Subgroup Analyses**

1451 A secondary analysis will assess whether the treatment group difference in the proportion of patients with surgical failure by 3 years varies in subgroups based on baseline factors.

1452 Interpretation of subgroup analyses will depend on whether the overall analysis demonstrates a significant treatment group difference. Subgroup analyses will be interpreted with caution, particularly in the absence of an overall treatment group difference.

1456

1457 The primary subgroups of interest are baseline monofixation status as determined using Titmus stereoacuity data, baseline monofixation status determined as using Preschool Randot stereoacuity data, and age. Other baseline factors which will be assessed in exploratory subgroup analysis are prior treatment, near stereoacuity, distance stereoacuity, control of IXT, whether a constant exotropia was present at distance, and quality of life. In accordance with NIH guidelines, a subgroup analysis of treatment efficacy according to gender, as well as race/ethnicity, will also be conducted.

1464

1465 The general approach for subgroup analyses will be to determine the proportion of patients with surgical failure for each treatment group within each subgroup, using the same method as for the primary analysis. Factors showing evidence of interaction with treatment effect will be formally assessed by including an interaction term in a Cox proportional hazards model that includes the factor. In general, power will be low for formally detecting interactions unless the interaction is very large.

1471

1472 **6.2.2 Surgical Failure Proportion at 3 Year Timepoint**

1473 The binomial proportion of patients who meet surgical failure criteria *at* the 3 year visit (as opposed to *by* the 3 year visit) will be estimated for each treatment group and compared using Fisher's exact test.

1476

1477 Patients who do not return for the 3 year visit will not be included in the analysis, including patients who met surgical failure criteria at an intermediate visit. Patients who complete the visit will be classified based on their status at 3 years, regardless of whether they met surgical failure criteria at an earlier timepoint, unless they have been re-operated (or treated with botulinum toxin), in which case they will be classified as a surgical failure.

1482

1483 The potential for bias in the treatment group comparison is recognized. Once a patient has met the clinical criteria for surgical failure criteria at an interim follow up visit, the decision to reoperate—and thus permanently classify the patient as a surgical failure for the analysis *at* 3

1485

1486 years—is at the discretion of an unmasked investigator and therefore could be related to
1487 treatment group. To assist in assessing for potential bias, the extent to which treatment group is
1488 related to the decision to reoperate will be evaluated.
1489

1490 **6.2.3 Success Proportion at 3 Year Timepoint**

1491 The estimated proportion of patients who meet criteria for ‘success’ at the 3-year outcome exam
1492 (section 6.1.1) will be calculated and compared between treatment groups using a Fisher’s exact
1493 test. A 95% confidence interval on the difference of proportions between the two groups also
1494 will be calculated.
1495

1496 The potential for bias in this treatment group comparison is recognized. Once a patient has met
1497 the clinical criteria for surgical failure criteria at an interim follow up visit, the decision to
1498 reoperate—and thus prevent the patient from being classified as a success for the 3 year
1499 analysis—is at the discretion of an unmasked investigator and therefore could be related to
1500 treatment group. To assist in assessing for potential bias, the extent to which treatment group is
1501 related to the decision to reoperate will be evaluated.
1502

1503 **6.2.4 Analysis of Secondary Outcomes**

1504 Additional secondary analyses will be performed to assess whether treatment group differences
1505 exist for secondary outcomes: near stereoacuity, distance stereoacuity, monofixation status as
1506 determined using Titmus stereoacuity data, monofixation status determined as using Preschool
1507 Randot stereoacuity data, development of amblyopia, and quality of life.
1508

1509 **6.3 Exploratory Analyses**

1510 **6.3.1 Exploratory Analyses in Primary Cohort**

1511 Exploratory analyses will be stratified by IXT type and conducted in the primary cohort (i.e.
1512 patients whose largest angle by PACT at enrollment is between 15 and 40 PD inclusive).
1513

1514 As exploratory analyses, the primary analysis comparing failure proportions by 3 years (section
1515 6.1), the comparison of failure proportions at 3 years (6.2.2) the comparison of success
1516 proportions at 3 years (6.2.3) will be repeated using the same outcome classification of surgical
1517 failure, success, or indeterminate as described section 6.1.1., with the following exception:

- 1518 • At the 3-year visit, for patients who are currently prescribed prism and/or deliberate
1519 overminus: the Preschool Randot at near score to be used for the outcome classification will
1520 be the one tested *without* wearing prism or overminus. If this measurement shows a decrease
1521 of at least 2 octaves (at least 0.6 log arcsec) from the enrollment measurement, or to nil, to
1522 avoid adding to testing burden and to the complexity of visits, a confirmatory retest *is not*
1523 needed to be considered a surgical failure for this analysis.

~~1524~~

1526 **6.3.2 Exploratory Analyses in Patients with Baseline Angle > 40 to 50 PD**

1527 Additional exploratory analyses will be stratified by IXT type and conducted in a secondary
1528 cohort of patients whose largest angle by PACT at enrollment is > 40 to 50 PD.
1529

1530 The proportion of patients with surgical failure by 3 years will be calculated and will be
1531 compared between treatment groups using the same method as for the primary analysis.
1532

1532

1533 **6.4 Safety Analyses**

1534 Postoperative complications will be tabulated according to treatment group.

1535

1536 **6.5 Additional Tabulations and Analyses**

1537 The following will be tabulated according to treatment group:

- 1538 1. Baseline demographic and clinical characteristics
- 1539 2. Baseline data for study completers vs. non-completers
- 1540 3. Protocol deviations

1541

1542 A flow chart will be constructed that accounts for all subjects. Visit completion rates will be
1543 tabulated according to treatment group for each visit. The percentage of subjects with visits
1544 completed in window, out of window, and missed for each visit will be tabulated.

1545

1546 **6.6 Interim Analysis**

1547 There are no plans to formally assess surgical failure at a timepoint earlier than 3 years because it
1548 is the long-term outcome that is of clinical interest and because the treatment groups are
1549 expected to differ in the timing of surgical failure and in the criteria met for surgical failure.

1550 Patients receiving unilateral lateral rectus recession with medial rectus resection (R&R) are
1551 expected to fail earlier, due primarily to consecutive esotropia (i.e., overcorrection) which cannot
1552 be managed with prism, whereas patients receiving bilateral lateral rectus recessions (BLRrec)
1553 are expected to have better short-term motor outcomes but fail later, due primarily to recurrence
1554 of the intermittent exotropia over the long term. A treatment group comparison of failure

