 - 885 • Testing of control must be performed by a pediatric ophthalmologist, pediatric
886 optometrist, or a certified orthoptist.
 - 887 • Testing must be done prior to dissociative testing or at least 10 minutes after such testing.
- 888 4. Ocular alignment testing:
- 889 • Strabismic deviations will be assessed in current refractive correction (either spectacles,
890 contact lenses, or a trial frame) by the cover/uncover test and then measured with the
891 Simultaneous Prism and Cover Test (SPCT) (if tropia is of sufficient duration to
892 measure) and Prism and Alternate Cover Test (PACT) in primary position at near (1/3
893 meter), distance (6 meters) and remote distance (at least 50 feet, e.g., out the window or
894 down a long hallway) (PACT only) as outlined in the IXT Testing Procedures Manual.
 - 895 • The deviation will be recorded as constant if a manifest tropia is present 100% of the time
896 during the examination, determined by at least 3 cover/uncover tests (one must be before
897 any dissociation), or as intermittent if a manifest tropia is present (including after
898 dissociation) but not 100% of the time during the entire exam. The magnitude of the
899 deviation may change (vary) independently of the frequency of the deviation; frequency
900 of tropia (constant vs. intermittent) is determined solely by whether the manifest tropia is
901 present all or some of the time, including after dissociation. If a tropia is not observed at
902 any time but a phoria is present, then the deviation will be recorded as not tropic (phoric
903 only). If no deviation is present at any time, 'no deviation' will be recorded.
 - 904 ○ If the child appears to have a constant tropia but shows excellent stereoacuity that
905 may be inconsistent with the diagnosis of constant tropia, the examiner should look
906 over the child's polarized glasses to determine whether the child is indeed
907 constantly tropic (by direct observation by cover/uncover test).
 - 908 • The deviating eye will be recorded as "right", "left", or "alternates."
 - 909 • Testing will be performed following control of exodeviation testing and prior to any
910 cycloplegia.
 - 911 • Ocular motility will be assessed including: ductions, oblique muscle dysfunctions,
912 dissociated vertical deviations, and nystagmus.
 - 913 • Ocular alignment testing must be performed by a pediatric ophthalmologist, pediatric
914 optometrist, or certified orthoptist.

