1.5 Complete or Near-complete Resolution at 3 Years

Complete or near-complete resolution at 3 years was defined post hoc as meeting all of the following at the 3-year visit:

1. Exodeviation <10 PD (tropia, phoria, or no deviation) by both SPCT and PACT at distance and near and ≥ 10 PD reduction in PACT magnitude from distance and near angles at enrollment provided the corresponding angle was at ≥ 10 PD at baseline.
 - This criterion was originally written as ≥ 10 PD reduction in PACT magnitude from *largest of* distance and near angles at enrollment. After asking the protocol chairs to clarify which angle needed to be reduced by ≥ 10 PD at 3 years in cases where the distance and near angles at enrollment are the same magnitude (i.e. neither is the ‘largest’), it was decided that both angles should be reduced by ≥ 10 PD in order to meet the criterion, if the angle was at ≥ 10 PD at baseline, OR should be reduced to orthodeviation (0 PD) if the angle was at <10 PD at baseline. *Note that because all patients in the basic primary cohort have distance and near PACT ≥ 10 PD, this caveat is not cited in the manuscript as being part of the criteria. Only one patient in one of the secondary cohorts was <10 PD at baseline—a 3 PD near angle which was ortho at 3 years.* The revised criterion was extended to all patients, not only those whose enrollment PACT was the same magnitude at distance and near, for consistency. For example, if a patient with 20 PD at distance and near at baseline is required to have a reduction ≥ 10 PD at both distance and near at 3 years in order to be eligible to meet complete or near-complete resolution, then a patient with 25 PD at distance and 15 PD at near should also be required to have both reduced by ≥ 10 PD at 3 years, otherwise the first patient is being penalized simply for having the same measurement at both distances.
2. Esotropia <6 PD (tropia or no tropia, *note that phoria does not apply to SPCT*) at distance and near by SPCT
3. No decrease in Preschool Randot stereoacuity of ≥ 2 octaves from the enrollment stereoacuity or to nil
4. No reoperation or treatment with botulinum toxin
5. No non-surgical treatment for a recurrent or residual exodeviation

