- 477 3. For each definition, compare proportion of participants with complete or near-complete resolution
- 478 at 3 years between treatment groups and calculate 95% CI.
- 479

480 **Technical Plan**

- 481
- 482 1. Complete or near-complete resolution AT 3 years without regard to previous failure (post hoc)
- 483 was defined as meeting all of the following at the 3-year visit:
- 484
- 485 1. Exodeviation <10 PD (tropia or phoria) by both SPCT and PACT at distance and near and
 - 486 either ≥ 10 PD reduction in 3-year PACT magnitude from both the distance and near
 - 487 preoperative* angles ≥ 10 PD if the corresponding preoperative angle was ≥ 10 PD, or reduction
 - 488 to orthodeviation by PACT if corresponding preoperative angle was <10PD. *Because all*
 - 489 *patients in the basic primary cohort had distance and near PACT ≥ 10 PD, the last phrase was*
 - 490 *not applicable and therefore not included in the definition in the manuscript.*
 - 491 2. Esotropia <6 PD at distance and near by SPCT
 - 492 3. No decrease in Preschool Randot of ≥ 2 octaves from enrollment stereoacuity or to nil
 - 493 4. No reoperation or treatment with botulinum toxin
 - 494 5. No non-surgical treatment for a recurrent or residual exodeviation (nonsurgical treatment for
 - 495 esodeviation was allowed)

496 **Preoperative angle represents the largest deviation by PACT at distance, near, and remote*

497 *distance at the enrollment visit if no additional preoperative (pre-randomization), PACT*

498 *measurements were taken closer to the surgery date; OR the PACT deviation entered on the*

499 *randomization form if any additional preoperative PACT measurements were taken closer to the*

500 *surgery date.*

- 501
- 502 Complete or near-complete resolution AT 3 years with no previous failure was defined as follows:
- 503 • Patients who had suboptimal surgical outcome at any time will be considered not resolved
 - 504 • All other patients will have same values as for complete or near-complete resolution AT 3
 - 505 years without regard to previous failure.
- 506

- 507
508
2. Calculate complete or near-complete resolution outcomes using baseline alignment (see note), 3-year alignment, 3-year stereoacuity, nonsurgical treatment for IXT during the study, reoperation

509
510

data. In addition, suboptimal surgical outcome **by** 3 years will also be used to calculate complete or near-complete resolution AT 3 years with no previous failure.

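### Protocol success and indeterminate overlap for esophoria of 6 PD or more, and the 2018 SAP carries the gap into complete or near-complete resolution

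*Protocol*

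**What the plan says.** Protocol 6.1.1 says that each patient's "condition will be classified as either surgical failure, success, or indeterminate as follows". For *success*, criterion 1 is "Exodeviation less than 10 PD (tropia or phoria) by PACT at distance and near and reduction of more than 10 PD" from the larger of the enrollment distance and near angles. Criterion 2 is "Esotropia less than 6 PD at distance and near by SPCT". The remaining criteria cover stereoacuity, reoperation or botulinum toxin, and nonsurgical treatment for IXT. No criterion mentions esophoria.

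*Indeterminate* requires preserved stereoacuity, no reoperation or botulinum toxin, and at least one of three alignment findings. The third of these is "Intermittent esotropia or esophoria ≥ 6 PD at distance and/or near", with no test named. Protocol 6.2.3 compares the success proportion between arms with Fisher's exact test.

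SPCT is conditional on a tropia. Protocol 2.5, item 4, provides for the "Simultaneous Prism and Cover Test (SPCT) (if tropia is of sufficient duration to" measure it); section 4.5, item 4, repeats the condition for the masked exams.

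The 2018 SAP, section 1.5, defines complete or near-complete resolution. Criterion 1 begins "Exodeviation <10 PD (tropia, phoria, or no deviation) by both SPCT and PACT at distance and near" and requires a PACT reduction of at least 10 PD at both distances. Criterion 2 limits esotropia to under 6 PD by SPCT, with the remark "note that phoria does not apply to SPCT". In the Objective #4 technical plan, criterion 5 reads "No non-surgical treatment for a recurrent or residual exodeviation (nonsurgical treatment for", and the parenthesis goes on to allow such treatment for esodeviation. Section 1.5 then says that the outcome differs from protocol success only in how an earlier failure is handled. The version without earlier failure is presented as consistent with the prespecified success criteria.

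**The concern.** The three classes are meant to be exclusive, yet one kind of child fits two of them. The success comparison in Protocol 6.2.3, and the resolution comparison that takes its place in the 2018 SAP, would count as good outcomes some children whom the protocol itself calls indeterminate.

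The limits are also uneven. Exodeviation is capped by PACT, which captures phorias. Esodeviation is capped only by SPCT, which does not. Protocol 6.6 expects R&R failures to come mainly from overcorrection and BLRrec failures mainly from recurrent exotropia, so a gap on the eso side might not fall equally on the two arms.

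A reader of the SAP would also take the no-previous-failure version for the protocol's own success outcome, because the text says that nothing else has changed.

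**Working it through.** **Step 1: one child through each rule.** Take baseline exodeviation 30 PD at distance and near. At 3 years there is no tropia and an esophoria of 14 PD at both distances; stereoacuity is kept, with no reoperation and no nonsurgical treatment.

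- Protocol success 1: no exodeviation of 10 PD or more. The reduction is 30 − (−14) = 44 PD if eso is negative, or 30 − 14 = 16 PD if unsigned. Both exceed 10, so it is met.
- Protocol success 2: no esotropia by SPCT, so it is met. Criteria 3 to 5 are met by construction.
- Protocol indeterminate: esophoria 14 ≥ 6 PD, stereoacuity kept, no reoperation. Met.
- 2018 SAP resolution: both reductions are at least 10 PD, there is no esotropia by SPCT, and the rest holds. Met.

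The child is both a success and indeterminate, and is a resolution under the SAP. The residual class in SAP 1.7 holds only non-reoperated children who meet neither suboptimal outcome nor resolution, so it cannot catch this child.

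An intermittent esotropia of 6 PD or more by SPCT does not overlap, because it fails success criterion 2. The overlap is confined to deviations that SPCT does not register as 6 PD or more.

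**Step 2: how large an esophoria can pass.** Let b be the baseline angle (equal at both distances) and e the esophoria.

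- Signed coding: reduction = b + e, which always exceeds 10 when b ≥ 15. There is no upper limit on e.
- Unsigned magnitude: reduction = b − e. The protocol's rule (more than 10) gives e < b − 10. The SAP's rule (at least 10) gives e ≤ b − 10.

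In whole PD, the esophorias of 6 PD or more that pass under unsigned magnitude are:

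| Baseline (PD) | Both success and indeterminate | SAP resolution |
|---|---|---|
| 15 | none | none |
| 16 | none | 6 |
| 18 | 6–7 | 6–8 |
| 20 | 6–9 | 6–10 |
| 25 | 6–14 | 6–15 |
| 30 | 6–19 | 6–20 |
| 40 | 6–29 | 6–30 |

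Under signed coding, every esophoria tested from 6 to 40 PD passes at every baseline from 15 to 40 PD. The only sign convention in either SAP is in the 2017 SAP, Objective #5, item 1a (exo positive, eso negative). It is given there for the 3-year PACT outcome, not for this reduction rule.

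**Step 3: the statement that only prior failure differs.**

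- Reduction: the protocol requires more than 10 PD from the larger of the distance and near angles. The SAP requires at least 10 PD at both.
- Nonsurgical treatment: the protocol bars it when given for IXT. The SAP bars it for recurrent or residual exodeviation and expressly allows it for esodeviation, which the protocol does not state.

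The sentence is therefore inaccurate on two counts apart from prior failure. The missing esophoria limit is not one of them, because protocol success lacks it too.

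**Step 4: size.** The documents give no count of esophoric children. The between-arm shift equals the share of R/R children reclassified minus the share of BLR children reclassified. Purely as assumptions:

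- 6% against 1% moves the difference by 5 points.
- 3% against 1% moves it by 2 points.
- Equal shares move it by 0.
- 1% against 3% moves it by 2 points the other way.

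For scale, assume 88 completers per arm (197 × 0.90 / 2 ≈ 88, using the protocol's 10% loss) and a proportion of 0.3. The standard error of the difference is then √(2 × 0.3 × 0.7 / 88) = 0.069, about 7 points. Each of these shifts is below one standard error.

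**The case against.** The strongest reply is that the planned test is still computable. Protocol 6.2.3 compares children who meet the success criteria, no analysis compares the indeterminate class, and the primary outcome is failure by 3 years. All of that is true and limits the point to secondary outcomes. It does not remove the conflict: following the success rule as written counts children whom the same section calls indeterminate.

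Criterion 1 might be read as requiring an exodeviation or no deviation, which would exclude esophoria. That fits poorly with a criterion 2 that tolerates esotropia under 6 PD and with a SAP that allows treatment for esodeviation.

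The treatment clause may be read as clarifying the protocol, whose criterion 5 concerns treatment for IXT and whose section 4.4.1 mandates prism for certain esotropia at 8 weeks. That is reasonable, and the SAP states the allowance openly. It also explains its change to the reduction rule. The inaccuracy lies in the sentence saying that nothing else differs.

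A reader might infer three stronger things that the documents do not support:

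- *The SAP chose to count overcorrection of any size as resolved.* It never mentions the overlap; it inherits the protocol's SPCT-only limit. Any size holds only under signed coding, and the SAP's reference to reduction to orthodeviation (0 PD) is compatible with an unsigned reading.
- *The comparison is tilted toward R&R.* Protocol 6.6 concerns early failure from consecutive esotropia that prism cannot manage. Such a child who meets the failure criterion and is reoperated cannot be a resolution. The section says nothing about pure esophoria at 3 years.
- *The primary result is affected.* Failure criteria do not involve esophoria.

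**Conclusion.** The point holds as a contradiction within the protocol's outcome classification, carried into the 2018 SAP by omission. It rests on two readings: that SPCT gives no value for a pure phoria, which the SAP itself notes, and that criterion 1 caps exodeviation without excluding esodeviation. How far it reaches depends on an unstated sign convention: no upper limit on esophoria if PACT is signed, and the baseline angle minus 10 PD if it is not. At a 15 PD baseline with unsigned magnitude there is no overlap.

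The success and resolution proportions may be somewhat too high, and the comparison may favour R&R. Neither the direction nor the amount can be established from the documents; the shifts in the working are illustrations. The separate finding, that the SAP misstates how its outcome differs from protocol success, needs no assumption about counts.

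**What to change.** 1. In Protocol 6.1.1 and in SAP 1.5 and Objective #4, state that a child meeting any protocol indeterminate criterion, including intermittent esotropia or esophoria of 6 PD or more with esophoria measured by PACT, is not a success or resolution. Apply this at least to the version described as consistent with prespecified success. A blanket PACT limit on all esodeviation is not equivalent. It would also remove a child with constant esotropia under 6 PD by SPCT but 6 PD or more by PACT, whom none of the indeterminate esodeviation wording covers.
2. State whether PACT is signed or unsigned in the reduction rule.
3. Correct the sentence on the sole difference so that it lists the changed reduction rule and the allowance for treated esodeviation.
4. Report the proportions under both the current and the corrected definition, and say that the correction came after the June 2017 closeout database named in the SAP.

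The threshold is the protocol's own, and PACT at distance and near is already collected at every masked exam, so no new data are needed. The cost is one more reported definition and a resolution proportion that may fall slightly.
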